4.6. Safety Variables

4.6.1. Adverse Events and Serious Adverse Events

Adverse events and serious adverse events will be collected from the time of informed consent signature and then at each visit until the end of the study with the exception of symptoms that occur in response to the EEU within 24 hours following the EEU. Asthmatic and allergic symptoms that occur in response to the EEU are not to be reported as AEs, as they will be recorded as outcome measures. However, AEs that occur in response to allergen exposure in the EEU that are outside of expected symptoms, including events which qualify as SAEs, up to 24 hours after EEU should be reported as AEs and SAEs as applicable.

All adverse events are to be coded to a “Preferred Term (PT)” and associated primary “System Organ Class (SOC)” according to the Medical Dictionary for Regulatory Activities (MedDRA, the Version 10 or the latest current available version).

An Adverse Event is any untoward medical occurrence in a patient or clinical investigation patient administered a pharmaceutical product and which does not necessarily have to have a causal relationship with this treatment.

A Serious Adverse Event is an adverse event (AE) that is classified as serious according to the criteria specified in the protocol.

Acute administration reactions are defined as any AE that occurs during the study drug administration or within 2 hours after the administration is completed. Infusion reactions must be reported as AEs and graded according to the NCI-CTCAE version 4.03 grading scale. Injection site reactions must be reported as AEs and graded according to the Food and Drug Administration (FDA) September 2007 Guidance for Industry, Toxicity Grading Scale for Healthy Adult and Adolescent Volunteers Enrolled in Preventive Vaccine Clinical Trials.

The severity of AEs that are not infusion reactions, or are not covered in the Toxicity Grading Scale for Healthy Adult and Adolescent Volunteers Enrolled in Preventive Vaccine Clinical Trials, will be graded according to the following scale:

- Mild: Does not interfere in a significant manner with the subject's normal functioning level. It may be an annoyance. Prescription drugs are not ordinarily needed for relief of symptoms, but may be given because of personality of the subject.
- Moderate: Produces some impairment of functioning but is not hazardous to health. It is uncomfortable or an embarrassment. Treatment for symptom may be needed.
- Severe: Produces significant impairment of functioning or incapacitation and is a definite hazard to the subject's health. Treatment for symptom may be given and/or subject hospitalized.

Laboratory results, vital signs, or ECG abnormalities are to be recorded as AEs if they are medically relevant: symptomatic, requiring corrective therapy, leading to treatment discontinuation and/or fulfilling a seriousness criterion.

The relationship of AEs to the EEU exposure will be assessed by the blinded investigator.

4.6.2. Adverse Events of Special Interest

No AEs of special interest are defined for this study.

4.6.3. Laboratory Safety Variables

The clinical laboratory data consists of serum chemistry, hematology, and other.

Clinical laboratory values will be converted to standard international (SI) units and grouped by function in summary tables. Conventional unit may be provided. Functions are defined as follows:

- Liver function including ALT, AST, alkaline phosphatase, gamma GT, total bilirubin (and, in case of values above the normal range, differentiation in conjugated and non-conjugated bilirubin),
- Renal function including creatinine, uric acid,
- Electrolytes including sodium, potassium,
- Metabolic parameters including total proteins, albumin,
- White blood cells (WBCs) including WBCs count and differential count (neutrophils, lymphocytes, eosinophils, basophils, monocytes),F
- Red blood cells and platelets including red blood cells count, hemoglobin, hematocrit and platelets count,
- Other

4.6.4. Vital Signs

Vital signs (temperature, pulse, blood pressure, and respiration rate) will be summarized by baseline and change from baseline to each scheduled assessment time with descriptive statistics.

4.6.5. 12-Lead Electrocardiography (ECG)

12-Lead ECG parameters include

P-R interval ,QT interval, QTc interval, QRS interval, Ventricular rate and Heart rate and etc..

QTcF and QTcB:

$$QTcF \text{ (ms)} = QT/RR^{1/3} \text{ and } QTcB \text{ (ms)} = QT/RR^{1/2},$$

Where QT is the uncorrected QT interval measured in ms, and RR is 60/HR with HR being the heart rate in beats per minutes.

4.6.6. Physical Examination Variables

A full or brief physical examination will be performed according to the site's procedures at the time points in [Table 1](#). The limited physical examination will include assessment of HEENT, respiratory, cardiovascular, dermatologic, and allergic/immunologic. The physical examination variable values will be indicated to be either normal or abnormal, clinically significant.

4.7. Pharmacokinetic Variables

Pharmacokinetic variables are total concentration of REGN1908, total concentration of REGN1909 and total antibody (REGN1908+REGN1909) in serum, at the sampling times specified in Section [10.2](#) (Appendix).

4.8. Immunogenicity Variables

The immunogenicity variables are ADA status, titer and time-point/visit. Serum samples for ADA will be collected at the clinic visits specified in Section [10.2](#) (Appendix).

4.9. Biomarker Variables

- Allergen-specific IgE levels (cat hair, Fel d 1) at screening visit 1 (V1) and baseline.
- Allergen-specific IgE levels (Fel d 2, Fel d 4, Fel d 7) at screening and baseline to assess sensitization status and to evaluate the relationship between response to REGN1908-1909 and poly/mono-sensitization ([van Ree, 1999](#)).

5. STATISTICAL METHODS

For continuous variables, descriptive statistics will include the following: the number of patients reflected in the calculation (n), mean, median, standard deviation, minimum, and maximum.

For categorical or ordinal data, frequencies and percentages will be displayed for each category.

5.1. Demographics and Baseline Characteristics

Demographics and baseline characteristics will be summarized by treatment group for the FAS. A listing of demographics and baseline characteristics will also be presented.

5.2. Medical History

Medical history will be based on the safety population.

Medical history will be summarized by primary SOC and PT for each treatment group. The table will be sorted by decreasing frequency of SOC followed by PT based on the overall incidence across treatment groups. Medical history will also be presented in a listing.

5.3. Prior/Concomitant Illnesses and Medications

Prior/concomitant illnesses and medications will be based on the safety population.

The number and proportion of patients taking prior/concomitant medications, and prohibited medications will be summarized, sorted by decreasing frequency of ATC Level 2 and ATC level 4, based on the overall incidence for the combined treatment groups. Patients will be counted only once for each medication class (ATC level 2 and 4) linked to the medication.

Concomitant treatments for asthma and allergic symptoms, including allowed and rescue treatments, will be analyzed similarly.

Concomitant medications used to treat EEU related events will be tabulated separately.

Listings of prior and concomitant medications will be provided.

5.4. Rescue/ Prohibited Medications

Rescue and prohibited medications will be based on both the efficacy and safety population.

The number and proportion of patients taking rescue medications at EEU exit, during the 6-hour observation period on-site and during the at-home monitoring period will be summarized for each treatment group and by type of rescue medication. The total dose of each rescue medication taken per patient will be calculated at each visit at EEU exit, during the 6-hour observation period on-site and during the at-home monitoring period, and will be summarized for each treatment group.

5.5. Subject Disposition

The following summaries will be provided:

Summary of total screened subjects, numbers of FAS, PPS and SAF by treatment and total. Summaries of discontinuations and/or dropouts by reasons and treatments will be presented.

If necessary, the discontinuations and/or dropouts will be compared among the treatment groups. If necessary, the mechanisms, (missing completely at random, missing at random, and non-ignorable) of the missing and/or dropouts will be explored.

5.6. Analyses of Efficacy Variables

The primary endpoint is the time to EAR upon day 8 Controlled Cat Allergen Challenge in an EEU. The time to EAR will be defined as the time to a $\geq 20\%$ reduction in FEV1 (adjudicated by the blinded investigators) or when the patient voluntarily departs the EEU due to clinically significant allergic and/or asthma symptoms. During the post-randomization allergen challenges, the patient may remain in the EEU for a maximum of 4 hours. If a patient does not experience an EAR and remains in the EEU for the maximum time, their time to EAR will be censored at 4 hours. Censoring implies that the time to EAR is at least 4 hours, but the exact time is unknown. The statistical model will be a cause-specific Cox's proportional hazards model to compare the hazard ratio of EAR on day 8 in REGN1908-1909-treated patients to placebo-treated patients. This model allows for covariate adjustment for allergen concentration in the EEU on day 8 and the patient's time to EAR during the baseline Cat Allergen Challenge. Under this model, the hazard ratio is directly related to the ratio of median duration of tolerated exposure in the current challenge test on day 8, where a hazard ratio of 1 implies that the median duration of tolerated exposure in the 2 treatment groups is the same. The following null and alternative hypotheses of the primary endpoint will be tested:

H0: The hazard rate of EAR during the day 8 Controlled Cat Allergen Challenge is the same in patients receiving REGN1908-1909 and placebo (hazard ratio, HR = 1)

H1: The hazard rate of EAR during the day 8 Controlled Cat Allergen Challenge is lower (ie, the median duration of tolerated exposure is longer) in the REGN1908-1909-treated patients as compared to placebo-treated patients (HR < 1)

5.6.1. Analysis of Primary Efficacy Variable(s)

The time to EAR for each treatment will be examined using Kaplan Meier estimates with patients being censored at 4 hours if they did not experience an EAR and remained in the EEU for 4 hours. If a patient leaves the EEU before experiencing an EAR and for reasons unrelated to their clinical symptoms, they will be censored at the time of EEU departure. The median time to EAR for each treatment group and the corresponding 95% confidence intervals will be presented for each Controlled Cat Allergen Challenge. A formal comparison of time to EAR in the treatment groups at day 8 will be performed using a Cox proportional hazards model, adjusting for allergen concentration in the EEU and time to EAR in the baseline Cat Allergen Challenge. In patients who receive EEU related medications (including medications given on-site and rescue medications taken at-home), the impact of the carryover of medications between challenges will be explored by including taking medication or not as baseline variable for the model of each subsequent visit. A one-sided 5% statistical test of the hazard ratio for placebo compared to drug will be performed.

If the Cox proportional hazards model does not converge, an extension of the Wilcoxon Rank Sum test comparing the ranks of time to EAR under censoring, adjusted by the covariates specified above, will be used ([LaVange and Koch, 2006](#)). As an additional sensitivity analysis, the presence or absence of an EAR within the 4-hour period in the REGN1908-1909 treatment group as compared to placebo will be tested using a Fisher's Exact Test.

Subgroup analyses may be performed by gender, age, baseline IgE and the ratio of Fel d 1 IgE to Cat Allergen IgE at baseline. The ratio of Fel d 1 IgE to Cat Allergen IgE at baseline (log transformed if the distribution is skewed) will also be explored as potential covariate in the Cox proportional hazards model.

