## 2.3. Exploratory Objective(s)

### 2.3.1. Exploratory Efficacy Objectives

- To evaluate LAR on days 8, 29, 57, and 85
- To evaluate whether a single prophylactic SC administration of REGN1908-1909 inhibits a wheal-and-flare response to a skin prick test with serial allergen titration with cat allergen in patients with cat allergen-triggered asthma and AR with or without conjunctivitis on days 29 and 85
- To evaluate the prophylactic efficacy of REGN1908-1909 in cat-allergic patients not living with a cat to reduce respiratory symptoms induced by a Controlled Cat Allergen Challenge on days 8, 29, 57, and 85 as measured by chest symptom questions
- To assess the prophylactic effect of REGN1908-1909 on biochemical measures of asthma control (FeNO) in patients with cat allergen-triggered asthma induced by a Controlled Cat Allergen Challenge on days 30 and 86 and measured 24 hours after challenge
- To assess the prophylactic effect of REGN1908-1909 on TNSS, TOSS, and chest symptoms up to 24 hours after leaving the EEU
- To assess the prophylactic effect of REGN1908-1909 on objective measures of nasal congestion (PNIF) in patients with cat allergen-triggered asthma induced by a Cat Allergen Challenge on 8, 29, 57, and 85
- To assess the relationship between baseline cat allergen-specific IgE levels (cat hair sIgE, Fel d 1 sIgE), total IgE, and the ratio of cat allergen-specific IgE/total IgE (cat hair sIgE/total IgE and Fel d 1-specific IgE/total IgE levels) and efficacy of REGN1908-1909
- To assess the relationship between cat allergen-specific IgE levels (Fel d 2, Fel d 4, Fel d 7, and other common allergens) at screening and baseline to evaluate the relationship between response to REGN1908-1909 and poly/mono-sensitization
- To assess the extent of REGN1908-1909 interference with the measurement of endogenous anti-Fel d1 IgE in baseline samples and its relationship to clinical benefit
- To assess the degree to which REGN1908-1909 prevents induction of type 2 inflammation in the nasal mucosa as assessed by RNA sequencing of nasal brushing on day 29.

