2.2. Sample Size and Power Considerations

The primary objective of this study is to assess the time to EAR in a Controlled Cat Allergen Challenge in patients receiving REGN1908-1909 compared to placebo-treated patients. Patients will be randomized (1:1) to receive placebo or REGN1908-1909. With 30 patients per treatment arm, an increase in median time to EAR from 58 minutes in the placebo-treated patients to 132 minutes in patients treated with REGN1908-1909 (ratio of median duration of tolerated exposure of 2.25 or, equivalently, hazard ratio of 0.44) can be detected with 84% power assuming a one-sided type I error of 0.05 and a 13% dropout rate (8 patients). A median time to EAR of 58 minutes was observed in untreated patients in the Alyatec validation study ([Gherasim, 2018](#)) and the ratio of median duration of tolerated exposure of 2.25 is based on the estimated effect size of Omalizumab observed in a previous Cat Allergen Challenge study performed in a live cat room ([Corren, 2011](#)). These estimates of drug effect from this live cat room challenge provide the closest data available for powering this study, as an interventional study has not previously been performed in an EEU with cat allergen. The sample size calculation was performed based on the log-rank test comparing the duration of tolerated exposure of 2 groups with the above-mentioned assumptions.

With 60 cat-allergic patients, this study also has 88% power to detect differences in the key secondary endpoint, percent change in the AUC of FEV1 induced by a Controlled Cat Allergen Challenge over the exposure interval from baseline to the Controlled Cat Allergen Challenge in patients treated with placebo as compared to REGN1908-1909. This power calculation assumes a mean AUC of 27 in the placebo-treated patients compared to 15 in patients treated with drug, based on a previous Cat Allergen Challenge study and a one-sided type I error of 0.05 ([Corren, 2011](#)). The primary analysis will be conducted on the full analysis set (FAS) population (Section 3.1).

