5.10. Analysis of Biomarker Data

All biomarker analyses will be performed on the FAS using all observed data. Descriptive statistics for the observed values and change and percent change from baseline in detectable IgE (or percent of detectable IgE compared to baseline) by treatment and visit will be provided for the biomarker variables.

The percent of detectable IgE at each visit compared to baseline, and the ratio of Fel d 1 IgE to Cat Dander IgE at baseline will also be correlated to the primary and secondary clinical efficacy endpoints using Spearman's rho test. Both the Spearman correlation coefficients and p-values will be reported.

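### The committed baseline IgE analyses measure prognosis, but the objective asks about effect modification, and the one route to that is an optional, undefined subgroup analysis

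*SAP*

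**What the plan says.** **Objective.** One item in Protocol 2.3.1 opens "To assess the relationship between baseline cat allergen-specific IgE levels". It adds total IgE and the ratios of cat hair and Fel d 1 specific IgE to total IgE, and ends by linking these to efficacy of the drug.

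**Cox model.** SAP 5.6.1 says of the baseline ratio of Fel d 1 IgE to cat IgE: "log transformed if the distribution is skewed) will also be explored as potential covariate in the Cox proportional hazards model". Protocol 10.4.3.1 has the same covariate, and SAP 5.6.3 repeats it for time to LAR. No treatment-by-ratio term is named. Where the SAP wants an interaction it says so, as with treatment-by-visit in 5.6.2 and 5.6.3.

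**Correlation.** SAP 5.10 states that "the ratio of Fel d 1 IgE to Cat Dander IgE at baseline will also be correlated to the primary and secondary clinical efficacy endpoints", by Spearman's rho. (It calls the denominator cat dander IgE; I take this to be the same ratio.) Biomarker analyses use the FAS. The descriptive statistics are to be given by treatment; the correlation sentence does not mention arm.

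**Subgroups.** SAP 5.6.1 permits, but does not require, subgroup analyses by baseline IgE and by this ratio. It gives no cut-point, interaction test or form of presentation. The summary table in SAP 10.1 enters No under subgroup analysis for time to EAR.

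**The concern.** A main-effect term assumes one drug hazard ratio at every value of the biomarker. A correlation taken across both arms asks whether the biomarker tracks the outcome in anyone. Both describe prognosis, so they can mislead in two ways. A ratio that predicts time to EAR equally on drug and placebo can look related to efficacy when the drug effect is constant. A ratio that does change the drug effect can be missed when its slopes in the two arms offset each other. At stake is whether this exploratory objective gets an interpretable answer, in a trial whose first-step analysis is meant to speed up the planning of later studies.

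**Working it through.** **Planning inputs (SAP 2.2 and 5.6).** Medians of 58 and 132 minutes ("ratio of median duration of tolerated exposure of 2.25 or, equivalently, hazard ratio of 0.44"), 30 per arm, 8 of 60 dropping out (26 per arm left), one-sided 0.05, censoring at 240 minutes.

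**Reproducing the plan's power.** With exponential times, P(event) = 1 − 2^(−240/58) = 0.943 on placebo and 1 − 2^(−0.44 × 240/58) = 0.717 on drug. Events: 26 × (0.943 + 0.717) = 43.2. Schoenfeld power: Φ(√(43.2/4) × |ln 0.44| − 1.645) = 85.4%, against the stated 84%. With a hazard ratio of 1/2.25 it is 84.7%. The planning model is reproduced closely enough to build on.

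**What each analysis estimates.** Let x be the standardised log ratio, with log-hazard slope b_P on placebo and b_D on drug. Effect modification is b_D − b_P. A main-effect Cox term fits a common slope, a weighted average of b_P and b_D. That average is non-zero when b_P = b_D (no modification) and near zero when b_D = −b_P (strong modification).

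**Simulation.** 4,000 trials per row, 26 per arm, drug hazard ratio 0.44 at x = 0, two-sided 5% tests. The hazard ratios per SD of x are assumptions, because the documents give none. Spearman is taken over both arms. Entries are % of trials significant.

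| Scenario (HR per SD of x) | Main-effect Cox | Spearman | Treatment × x | Treatment × median split |
|---|---|---|---|---|
| No effect of x | 6.2 | 5.7 | 6.3 | 5.7 |
| Prognostic only, 1.5 | 69.5 | 54.7 | 5.8 | 6.6 |
| Prognostic only, 2.0 | 97.7 | 92.4 | 5.6 | 6.1 |
| Opposite, 1.5 placebo, 1/1.5 drug | 6.2 | 4.5 | 69.6 | 51.1 |
| Opposite, 2 placebo, 1/2 drug | 7.3 | 4.2 | 97.8 | 87.7 |
| Drug arm only, 1/1.5 | 19.2 | 16.3 | 25.9 | 17.4 |
| Drug arm only, 1/2 | 41.0 | 38.2 | 54.3 | 36.4 |

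**Sensitivity of the prognostic rows.** These runs omit baseline time to EAR, which is in the planned Cox model, and the entry requirement of an EAR within 2 hours. In a variant with a log-time slope of −0.5 per SD in both arms, the main effect is flagged in 84% of trials and Spearman in 70%. Adding both features, letting x also act on baseline time, and assuming a between-patient SD of 0.7 on log time lowers these to 50% and 48%. Without that heterogeneity the main-effect figure stays near 82%. At slope 0.3 with heterogeneity they are about 25% and 22%.

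**Precision of an interaction.** Its standard error is roughly 2/√43.2 = 0.304, so a 95% interval multiplies and divides the ratio of hazard ratios per SD by exp(1.96 × 0.304) = 1.8. Approximate power is Φ(|ln θ| × √(43.2/4) − 1.96) for a ratio of hazard ratios θ: 76% at 2.25 and 85% at 2.5, so 80% needs about 2.3-2.4 per SD. The simulation gives 69.6% at 2.25, so this is slightly optimistic.

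**The case against.** Several points on the other side stand.

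- A reader might infer that the ratio is examined only through a main effect and a correlation. SAP 5.6.1 does not support that: it allows subgroups by this ratio, and comparing drug effects across them would address modification. What remains is that the route is optional and undefined, and that table 10.1 does not list it.
- A reader might take it as settled that the Spearman correlation pools the arms. SAP 5.10 does not say so. It is the natural reading, and the Spearman figures above depend on it.
- The ratios in the Protocol 2.3.1 objective are specific to total IgE, not Fel d 1 to cat IgE. Covariate adjustment is a legitimate use of the latter, and the SAP does not present it as the test of that objective. But no SAP efficacy analysis names the specific/total ratios either. Protocol section 1 sends exploratory objectives to a separate biomarker report, so the SAP may not be the whole plan.
- Opposite slopes are the extreme case. With log-time slopes of −0.5 and +0.5, the drug effect, ln(132/58) + x = 0.82 + x, vanishes at x = −0.82, so the drug would shorten time to EAR in about 21% of patients. For a modifier in the drug arm only, the interaction test gains little and often misses too.
- It might be inferred that a correlation will be reported as effect modification and used to select patients. No section says so.

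None of this makes the committed analyses estimate how the drug effect varies with baseline IgE.

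**Conclusion.** The point holds as a mismatch between an exploratory objective and the methods committed to it. In the scenarios run, the planned analyses flag a purely prognostic ratio in about 50-98% of trials for moderate to strong effects. The rate is lower if the effect is weaker or if baseline time to EAR absorbs part of it. They detect an opposite-direction modifier in about 4-7%. For a drug-arm-only modifier the interaction test finds 26-54%, against 16-41% for the planned analyses. These sizes rest on assumed biomarker effects, exponential times and a Spearman correlation over both arms. The algebra on what each term estimates does not depend on the effect sizes. The primary day 8 comparison and the secondary treatment comparisons are untouched, so this is an inexpensive improvement and not a threat to the trial's main conclusion.

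**What to change.** 1. In SAP 5.6.1 and 5.10, add an exploratory treatment-by-log(ratio) term, alongside the ratio's main effect, to the Cox model and the MMRMs.
2. Do the same, each in a separate model, for baseline cat hair, Fel d 1 and total IgE and for the specific/total IgE ratios named in Protocol 2.3.1.
3. Report the treatment effect with its confidence interval at chosen percentiles (for example the 25th and 75th), as an estimate and not a pass/fail test.
4. Report the baseline-ratio Spearman correlations by arm and label them descriptive. A by-arm correlation does not show modification either: in the drug arm alone it was significant in 32.0% of trials with a purely prognostic ratio (1.5 per SD) and in 32.3% with a drug-arm-only modifier (1/1.5 per SD).
5. Reconcile the subgroup statement in SAP 5.6.1 with the No in table 10.1. If subgroups are kept, state the cut-point. In the table above a median split loses power against the continuous term.

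The cost is a few extra model fits on data already collected. The drawback is that at about 43 events the estimates are imprecise, and several are produced with no multiplicity control, so they must stay exploratory.
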